 - Lipid lowering medications such as: bile acid sequestrants (Cholestyramine, Colestipol, Colesevelam, etc.), cholesterol absorption inhibitors (Ezetimibe-Zetia), and fibrates (Gemfibrozil, Clofibrate, Fenofibrate, Triclor). Exceptions to this exclusion are HMG-CoA reductase (Statins).
 - On or planning to participate in a weight loss program.
 - Weight loss or weight gain greater than 10 lbs in the past 6 months.
 - History of eating disorders, anorexia, bulimia, or binge-eating in the past 5 years.
 - Participation in any regular endurance exercise: running, biking, aerobics (except walking) or resistance training greater than 2.5 hours per week.
 - Regular use of acid lowering medications (greater than 3 times per week) such as antacids, PPIs (proton pump inhibitors), or H2 blockers.
 - Unstable thyroid disease.
 - Psychiatric disorders including schizophrenia, bipolar, major depression or psychosis.
 - Antidepressant medication: SSRIs (selective serotonin reuptake inhibitors), SNRIs (serotonin norepinephrine reuptake inhibitors), MAO inhibitors, or TCAs.
 - Cancer of any type (except for non-melanoma skin) in the past 5 years.
 - Use of chemotherapeutic agents.
 - Pregnancy, planning to become pregnant during the study period, or breastfeeding.
 - Unwilling to use effective birth control during study.
 - History of bilateral mastectomy with nodal dissection.
 - Alcohol use, on average, greater than 3 servings per day, 20 servings per week (Serving size: 12oz beer, 4oz wine, 2oz hard liquor), or self-reported binge drinking.
 - Uncontrolled hypertension (HTN) determined at the discretion of the study MD or RN. HTN medications allowed in the study: angiotensin converting enzyme (ACE) inhibitors, calcium channel blockers, and diuretics.
 - Medications for chronic obstructive pulmonary disease (COPD) or kidney disease.
 - α -adrenergic or β -adrenergic blockers (oral or ocular) and diuretics.
 - Renal or chronic kidney disease due to any condition, renovascular disease, or dialysis.
 - Chronic liver disease such as hepatitis B, hepatitis C, or cirrhosis.
 - Cardiovascular disease including: myocardial infarction, cerebrovascular disease (CVA), coronary artery bypass graft, stenosis greater than 50%, angina, coronary artery disease (CAD), congestive heart failure (CHF), peripheral vascular disease (PVD) or dysautonomia.
 - History of autoimmune diseases such as rheumatoid arthritis, lupus, multiple sclerosis, vitiligo, or psoriasis.

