To calculate the dose of 360 mg EMIQ/day that participants will receive, we used the dose administered in the previous human studies from Japan as a benchmark. We wanted the dose in our study to reflect the greater average predicted weight of our participants compared to a person in the Japanese study due to an increase in BMI range for our study. The BMI range for the study completed in Japan was 24-31, while the range for this study is 26-37. Japanese study subjects weighed approximately 72kg while our prediction is that participants will average 94kg based on our database records. This % difference (31%) is reflected in the increase from 275mg/day to 360mg/day.

Our rationale for setting a minimum weight requirement is that a subject may be within the BMI range outlined in the study, but still not weigh enough to meet the ADI of 4.89mg/kg BW/day. A minimum bodyweight of 74kg should place participants in a safe range below the specified ADI. We believe that a minimum body weight of 74kg should be a requirement for study participation. This rationale is demonstrated in the following calculation:

$$\begin{aligned}4.89\text{mg/day} \times (x)\text{kg} &= 360\text{mg} \\(x)\text{kg} &= 360/4.89 \\(x)\text{kg} &= 73.62 \text{ (162.3lbs)}\end{aligned}$$

This study will be carried out after review and approval of the Institutional Review Board (IRB) of Tufts University. Following IRB approval, a total of 50 male and female volunteers will be recruited and admitted to the study. The scope and plan of the study will be described to the admitted volunteers and a written consent will be obtained before enrolling the subjects into the study. The study is planned to start in 2016 (i.e., begin enrollment) and volunteer activity completed within one to one and a half years.

The admitted volunteers will be scheduled and asked to come to the Metabolic Research Unit (MRU) at Jean Mayer USDA Human Nutrition Research Center on Aging (HNRCA) at Tufts University at the beginning of the study for enrollment (visit 1), baseline (visit 2), 4 weeks after baseline (visit 3), a visit 8 weeks after baseline (visit 4), and the final visit after 12 weeks (visit 5) for a total of 5 visits. Overnight fasted blood samples will be collected at screening and visits 2, 3, 4 and 5.

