Screening: Volunteers that were pre-screened by telephone will be scheduled and asked to come to the MRU at the HNRCA. Volunteers will be asked to arrive fasted for 12 hours. When they arrive, volunteers will be given a Screening Consent Form along with an explanation of all procedures that will be completed at screening. Volunteers will have an opportunity to read the consent form and have any of their questions answered to their satisfaction. Once their consent is given we will begin by measuring volunteer’s vital signs, height, body weight wearing a pre-weighted pair of scrubs, and BMI. Blood samples will be collected for blood chemistry analysis. Women of childbearing potential will be subjected to a blood pregnancy test. The Beck Depression Inventory will be administered to assess for depression. Additionally, study inclusion and exclusion criteria and health history will be reviewed. Breakfast and a \$25 screening stipend will be provided once screening procedures are complete. All subjects will be mailed a copy of screening labs within 1-2 weeks following the screening visit. Volunteer’s enrollment eligibility will be determined based on meeting inclusion and exclusion criteria. Subjects with abnormal hematologic parameters, as defined by the HNRCA Nutrition Evaluation Laboratory (NEL) reference ranges, which are determined by the study physician to interfere with study outcomes, will be excluded from study participation. At the discretion of the study physician, subjects will be alerted to abnormal results that warrant follow-up with their primary care physician. Subjects with abnormal hematologic values outside the NEL reference range that do not affect study outcomes will be included at the discretion of the study physician. Note that data generated from blood draws at this visit will be used as baseline values in lieu of drawing additional blood at visit 2 for subjects that continue the study after screening.

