Week 12, Visit 5: Subjects will be asked to return to the MRU approximately 12 weeks from their baseline visit or 4 weeks (\pm 1 week) from their previous visit. Subjects will be asked to arrive fasted for 12 hours and to bring back their unused supplement and compliance calendar. Vital signs, scrub weight and changes to volunteer health, medication and eligibility status will be assessed. Blood samples will be collected and archived pending tissue banking consent. Final measurements will be taken during this visit including: routine health screening analysis, lipid profile, adiponectin, insulin test, a urine dip stick, liver and kidney function (SGOT, SGPT, BUN, creatinine, and calculated GFR), skin fold thickness and waist/hip circumference. Subjects will be asked to rest for 30 min prior to measuring systolic and diastolic blood pressures and RMR analysis, which will be conducted by study staff. After RMR and BP measurements, subjects will be escorted to the BCAC for a whole body DXA scan to measure total and segmental body fats. A three factor eating questionnaire, food craving questionnaire, and the PAR will be administered to assess changes in volunteer's dietary inhibition, restraint, hunger, cravings and activity level throughout the study. Compliance with supplement intake will be determined by counting the unused capsules remaining in blister pack and by reviewing the compliance calendar. A continental breakfast meal will be provided to the subjects. Subjects will be mailed a \$305 check for completion of the final study Visit 5.

Below is an outline of the visits mentioned above:

Visit	Procedures	Length
Screening	Obtain Vital Signs Height, Scrub Weight and BMI 10mL Blood Draw* Urine Sample Review Inclusion/ Exclusion Criteria Review Health History Complete Beck Depression Inventory *Some women may be required to give an additional 3mL blood for a pregnancy test	2 Hours
Visit 1	Assess Health/Medication/Eligibility Changes Receive Instructions/Materials for Dietary Recalls	1 Hour
Between Visits 1 and 2	No visit required. Volunteers will be called 3x for 24-hour dietary recalls.	
Visit 2	Assess Health/Medication/Eligibility Changes Obtain Vital Signs Height, Scrub Weight and BMI Undergo EKG Measurement Urine Sample 30 Minutes Bed Rest Followed By RMR Measurement Hip/Waist Circumference Skinfold Thickness 17mL Blood Draw DXA Measurement Administer Questionnaires Receive Supplement/Instructions/Compliance Calendar	5 Hours

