Although employees will not be targeted for recruitment and enrollment, employees of Tufts University and/or the HNRCA (employee-subjects) who voluntarily want to participate in the study will be eligible for screening and enrollment. In order to qualify for the study, employee-subjects must respond to IRB-approval advertisement of their own accord and will not be directly approached by any person seeking to recruit them for participation in the study. Members of the research team, as direct-report subordinates of the PI and anyone who is direct-report subordinate to any of the research team members in any other capacity will not be eligible to participate in the study. If employee-subjects qualify to participate in the study, they cannot participate as volunteers during hours in which they are being compensated by Tufts University for their regular work. This includes use of vacation, personal days and sick time.

Interested subjects will be pre-screened by telephone. Potentially eligible subjects will be invited to screen in-person for the study in order to further determine eligibility. During the screening visit, informed consent will be obtained by authorized MRU personnel using the screening informed consent form. The consent interview will take place in a private area in the MRU at the HNRCA. Once all of the participant's questions and concerns have been addressed, the

designated staff will obtain informed consent. Subjects will then undergo routine blood and urine tests. If subjects meet study criteria, they will be invited to participate in the main study. Results of the blood and urine testing will be available at least 1-2 weeks after screening. Subjects with lab values that do not meet eligibility requirements, assessed by the study physician or nurse, will be disqualified and may be provided with a recommendation to see their physician. Prior to study enrollment, subjects will be allowed to read the main study consent form. Once all of their questions and concerns are addressed, and they understand all procedures in the study, a designated staff member will obtain their informed consent using the main study informed consent form.

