*Note: Non-English speaking individuals will not be enrolled in this study. The reasons being include the following: The HNRCA is not a health care facility, and does not have appropriate interpretive services to include non-English speakers. The standardized questionnaires have not been validated in other languages. This study will not directly benefit participants.

IV. Study Assessments

Blood and Spot Urine Collection: The MRU will collect a total of 60mL (12.2 teaspoons) of blood and three separate urine samples from each subject to measure the following:

Hematological measures: Complete blood count with auto-differential, white blood cell (WBC), red blood cell (RBC), hemoglobin (Hgb), hematocrit (Hct), platelet (Plt), Mean corpuscular volume (MCV), mean corpuscular hemoglobin (MCH), and mean corpuscular hemoglobin concentration (MCHC). WBC/Differential includes: neutrophils, lymphocytes, monocytes, eosinophils, and basophils.

Lipid profile: Triglycerides, Total Cholesterol, HDL-Cholesterol, LDL-Cholesterol.

Metabolic and hormonal markers: Insulin, adiponectin in serum, and urine stick test (Includes: total protein, glucose, urobilinogen, bilirubin, ketone, pH, occult blood).

Liver function: Aspartate aminotransferase (AST), alanin aminotransferase (ALT), alkaline phosphatase (ALP), gamma glutamyltransferase (GTP), total bilirubin (T-bill), lactate dehydrogenase (LDH), total protein (TP), and Albumin (Alb).

Muscle Function: Blood urea nitrogen (BUN), and creatine (Cre).

Electrolytes: sodium (Na), potassium (K), chloride (Cl), calcium (Ca), magnesium (Mg).

Blood and Urine will be collected according to the following scheme:

Screening: 13mL (2.6 teaspoons) of blood will be drawn at this visit. 5mL (1 teaspoon) will be drawn for complete blood count (CBC) with differential, and another 5mL (1 teaspoon) for routine blood chemistries. CBC measures will be used as baseline values. Additionally, participants in the screening process will be required to provide a spot urine sample for urinalysis. A 3mL (0.6 teaspoons) blood sample will be taken from women of childbearing potential at enrollment in order to conduct hCG testing. This test will determine whether the participant is pregnant, and thus ineligible for participation in this study.

Main Study:

Visit 1, Enrollment: No blood will be drawn during this visit.

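### The pregnancy exclusion covers the whole study period, but the only pregnancy test listed is one blood hCG at screening

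*Protocol*

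**What the plan says.** The Exclusion Criteria (Protocol III.C) list "Pregnancy, planning to become pregnant during the study period, or breastfeeding" and, separately, "Unwilling to use effective birth control during study". The first of these looks forward over the study period as well as at entry.

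The timing of the test is given in three places:
- The screening narrative (III.E.I Overview) says "Women of childbearing potential will be subjected to a blood pregnancy test".
- The visit outline in the same section carries a footnote to the screening row: "Some women may be required to give an additional 3mL blood for a pregnancy test".
- The blood collection scheme (III.E.IV Study Assessments), within its Screening paragraph, says a "blood sample will be taken from women of childbearing potential at enrollment in order to conduct hCG testing". A few lines later it says "Visit 1, Enrollment: No blood will be drawn during this visit".

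The Overview agrees that visit 1 has no draw: "Overnight fasted blood samples will be collected at screening and visits 2, 3, 4 and 5".

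Supplement is first dispensed at visit 2. DXA scans are done at visits 2 and 5, and urine is collected at both of those visits. The analytes listed for the urine dip stick do not include hCG. On how long screening results take, III.E.III says "Results of the blood and urine testing will be available at least 1-2 weeks after screening".

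**The concern.** An exclusion that runs through the study is tested once, before the participant is exposed to anything. Supplement and the first X-ray scan come at visit 2, an unstated time after screening, and the second scan comes about 12 weeks after that. A conception after screening, or one too early for the screening sample to detect, would not be picked up by any test in the protocol.

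The main stake is participant protection: the sponsor's own criterion is not checked by test when exposure starts or at either scan. There is a smaller data issue. Pregnancy would change weight and body composition, the SAP analyses everyone who completes, and neither document says how a participant found to be pregnant after visit 2 would be handled in the analysis.

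The enrollment wording adds an avoidable doubt about when an eligibility test is done.

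**Working it through.** **Step 1. How many hCG samples are planned?** The stated total of 60 mL per participant (III.E.IV) can be rebuilt from the itemised draws:

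- Screening: 5 (blood count) + 5 (chemistry) + 3 (hCG) = 13 mL
- Visit 1: 0 mL
- Visit 2: 10 + 7 = 17 mL
- Visit 3: 5 mL
- Visit 4: 5 mL
- Visit 5: 3 (blood count) + 10 + 7 = 20 mL

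Sum: 13 + 0 + 17 + 5 + 5 + 20 = 60 mL, which reproduces the stated figure. The visit outline agrees: 10 + 3 (footnote) + 17 + 5 + 5 + 20 = 60 mL. Without the hCG sample the sum is 60 - 3 = 57 mL. With two more 3 mL samples it would be 60 + 6 = 66 mL. The total therefore allows exactly one blood hCG sample, and it falls in the screening draw.

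**Step 2. Is there a test anywhere else?** Each tube at visits 2 to 5 has a stated purpose: liver and kidney function, insulin, adiponectin, lipids or blood count. None is for hCG. The dip stick covers protein, glucose, urobilinogen, bilirubin, ketones, pH and occult blood. The visit 5 narrative mentions a routine health screening analysis without itemising it, but the visit 5 tubes contain no hCG.

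**Step 3. How old is the test at each exposure?**

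- Screening to visit 2: about 1 to 2 weeks or more, taking the results lag in III.E.III as the floor. Visit 1 and three dietary recalls also have to fit in before visit 2. No maximum is stated. The floor is approximate, because the screening narrative has labs mailed within that same span.
- Visit 2 to visit 5: three intervals of 4 weeks, each ± 1 week. Nominal 3 × 4 = 12 weeks, shortest 3 × 3 = 9, longest 3 × 5 = 15.
- Screening to the second scan, using the 1 to 2 week floor: nominal 13 to 14 weeks, shortest windows 10 to 11, longest windows 16 to 17.

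**Step 4. How many conceptions might there be?** The documents give no sex mix and no conception rate, so both inputs are assumptions: 20 to 30 women of childbearing potential, and 0.1% to 0.5% per month over about 4 months.

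- Low: 20 × 0.001 × 4 = 0.08
- High: 30 × 0.005 × 4 = 0.6

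These count all conceptions. Those that are unrecognised or unreported, which are the ones a test would add, are fewer. With 1:1 allocation about half would be on EMIQ: 0.08 / 2 = 0.04 to 0.6 / 2 = 0.3.

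**The case against.** The best case for the plan is that other safeguards exist and that the wording conflict has little practical effect. Much of this stands.

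- **Wording.** A reader might infer that the test could be missed, or that a second one is meant at visit 1. The documents do not support either. The sentence sits in the Screening paragraph, its 3 mL is in the 13 mL screening draw, and two other places say screening. On its own this is a clerical slip.
- **Other checks.** A reader might infer that a woman who conceives after screening passes every check. She does not necessarily. Women unwilling to use birth control are excluded, premenopausal women must have a regular cycle, eligibility and health status are reviewed at visits 1 to 5, and weekly phone or email contact refers reported problems to the study physician. The exclusion is monitored after screening. What is missing is a test, so the gap is limited to pregnancies that are unrecognised or unreported.
- **Harm.** A reader might infer that each case would be a safety event. The documents do not say so. The Risk/Benefit Assessment (III.D) puts the DXA dose at 0.73 days of background radiation, EMIQ is described as generally recognised as safe, and about half of participants receive placebo. Nor does the protocol state that the exclusion exists because of the scans.
- **Interval.** A reader might add the 30 days without exercise to the gap between screening and visit 2. The protocol places that period before participation and does not say it follows screening, so it is not counted here.
- **Consent forms.** These are not among the documents reviewed and may hold instructions about pregnancy.

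None of these points supplies a test at visit 2 or visit 5, or a limit on the time from screening to visit 2.

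**Conclusion.** The point holds, and it is minor. One hCG test is listed, at screening. None is listed when supplement is first dispensed or at either DXA scan, and no maximum interval from screening to visit 2 is stated. The count of tests and the visit timing come directly from the protocol, and the blood total confirms them.

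The size is small. Fewer than one conception is expected, on an assumed number of women and assumed rates, and fewer still would go unnoticed. Even the upper figure of 0.6 in 50 completers would have little effect on the group comparison. The reason to act is that a cheap check would align the sponsor's own exclusion with the visits where exposure occurs.

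**What to change.** 1. In III.E.IV, correct the enrollment wording so that it agrees with the screening narrative and visit outline on when the hCG sample is taken.
2. Reconcile the pregnancy exclusion with the timing of its check. For women of childbearing potential, add hCG to the tests run on the urine already collected at visits 2 and 5, ahead of the DXA scans, and update the visit narrative, the visit outline and the urine analyte list to match. How a positive result is handled stays with the study physician under the protocol's existing provisions.

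The cost is a small amendment, one test strip per applicable woman at two visits, a few minutes of staff time and an occasional false positive to confirm. No new sample is needed and the 60 mL blood total does not change. The visit 5 test comes at the end of supplementation, so it serves the second scan and the interpretation of that visit's data. Between visits 2 and 5 the exclusion would still rest on review and contact.
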